Data will be obtained from nationwide, electronically recorded, population-based registers with prospective data collection. In particular, the IVF register in each country will be used to establish the study population. The IVF registers hold comprehensive information on ART treatments conducted at all fertility clinics, publicly- and privately-operated, in Denmark and Sweden, respectively. The study will therefore enable inclusion of information on IVF treatments among the entire female population of each country. The unique personal identification number assigned to individuals at birth or immigration in each country further allows for linkage of individual-level data across multiple registers and subsequently the creation of country-specific customized study databases. Data will be obtained on IVF/ICSI treatment characteristics, dispensed prescription drugs (including exposure to the study drugs, GnRH protocol used, etc.), pregnancy and other treatment outcomes, medical history, laboratory test results (Denmark only), and costs. The contents, set-up and structure of each national register is similar across the two countries, including coding classification systems such as the International Classification of Diseases, 10th revision (ICD-10) and the Anatomical Therapeutic Chemical (ATC) classification system. The same type of analyses can therefore be performed in both countries, with little need for adaptation. Individual-level data will be analyzed separately for each country. Meta-analysis may be used, as appropriate, to provide summary estimates for the entire study population across both countries.

[figure not shown]

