Date of pregnancy test	Continuous	N/A (used to derive outcome variable)		
Pregnancy test result or indicator for pregnancy	Continuous	N/A (used to derive outcome variable)		
Date of ultrasound	Continuous	N/A (used to derive outcome variable)		
Date of pregnancy loss	Continuous	N/A (used to derive outcome variable)		
Other clinical characteristics				
Height/weight or BMI	Continuous	X	X	
Obesity	Categorical	X	X	
Bariatric surgery	Categorical	X	X	
Smoking status*	Numerical	X	X	

Variable	Measurement scale	Baseline characteristic	Candidate variable for PS	Candidate variable for additional adjustment
Type 1 diabetes mellitus	Categorical	X	X	
Type 2 diabetes mellitus	Categorical	X	X	
Antidiabetic drugs	Categorical	X	X	
History of thromboembolic events	Categorical	X	X	
Use of thrombosis prophylaxis	Categorical	X	X	
Porphyria and other relevant conditions [#]	Categorical	X	X	
History of any cancer	Categorical	X	X	
Medical history, fertility-related				
Number of previous failed COS	Categorical	X	X	
History of failed IUI	Categorical	X	X	
History of COS with a study drug	Categorical	X	X	
History of COS with a non-study drug	Categorical	X	X	
Previous delivery with at least one live birth following IVF	Categorical	X	X	
Parity	Categorical	X	X	
OHSS	Categorical	X	X	
Amenorrhea or oligomenorrhea	Categorical	X	X	
PCOS	Categorical	X	X	
Endometriosis	Categorical	X	X	

Variable	Measurement scale	Baseline characteristic	Candidate variable for PS	Candidate variable for additional adjustment
Female infertility diagnosis	Categorical	X	X	
Female factor infertility*	Categorical	X	X	
Male factor infertility*	Categorical	X	X	
Idiopathic factor infertility*	Categorical	X	X	
Medical history, laboratory test results (value at most recent record on or prior to stimulation cycle index date) [†]				
Anti-Müllerian hormone, pmol/L	Continuous	X	X	
FSH, IU/L	Continuous	X	X	
Thyrotropin, mIU/L	Continuous	X	X	
Prolactin, mIU/L	Continuous	X	X	

BMI: body mass index; COS: controlled ovarian stimulation; FET: frozen embryo transfer; FSH: follicle-stimulating hormone; GnRH: gonadotropin-releasing hormone; ICSI: intracytoplasmic sperm injection; IUI: intrauterine insemination; IVF: in vitro fertilization; IU: international unit; L: liter; mIU: milli-international unit; OHSS: ovarian hyperstimulation syndrome; PCOS: polycystic ovarian syndrome; pmol: picomole; PS: propensity score.

Notes:

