[†]Not available in Denmark and available from 2015 in Sweden; can be approximated by subtracting the date of follicular aspiration from the date of embryo transfer for stimulation cycles.

* Available for Denmark only (from the DIVF).

Full list of conditions to be considered is provided in Appendix 3 (Section 14.3.3).

[‡] Available for Denmark only [from the Danish Register of Laboratory Results for Research (RLRR); see Section 9.4.1]. Because completeness is uncertain, these data will be used in a sensitivity analysis only, as described in analysis 4 in Table 8.

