9.9.3 Confounding by Baseline Characteristics

Confounding by baseline characteristics is a key challenge in non-interventional studies of drug treatment effects. Although the study drugs are equally recommended in IVF treatment guidelines and used interchangeably, differences in baseline characteristics, e.g., in terms of cause of infertility or previous IVF treatment, between the study cohorts cannot be ruled out. To minimize the potential for confounding, IPTW methods accounting for a broad range of characteristics, including history of IVF treatment, fertility-related health characteristics, and other factors potentially associated with the study outcomes will be applied.

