Antidiabetic drugs	ATC: A10*	Insulins and analogues, blood glucose lowering drugs, other drugs used in diabetes
Any cancer	ICD-10: C00-C97*	Malignant neoplasms
Porphyria	ICD-10: E80*	Disorders of porphyrin and bilirubin metabolism

Variable	Code ⁺	Comment
Amenorrhea or oligomenorrhea	ICD-10: N91*	Absent, scanty and rare menstruation, excluding ovarian dysfunction
PCOS	ICD-10: E28.2	
Endometriosis	ICD-10: N80*	
Pituitary insufficiency	ICD-10: E23*	
Female infertility	ICD-10: E28.3, E28.8, E28.9, N97*	Primary ovarian failure, other specified ovarian dysfunction, ovarian dysfunction unspecified, female infertility (excluding female infertility associated with male factors)
Thyroid disease	ICD-10: E00*-E07*	Disorders of thyroid gland
Parathyroid diseases	ICD-10: E21*, E20*	Hypoparathyroidism, hyperparathyroidism
Disorders of adrenal gland	ICD-10: E24.0, E26*, E27* (excluding E27.2, E27.3, E27.5)	Pituitary-dependent Cushing disease, hyperaldosteronism and other disorders of adrenal gland, including Addison disease
Polyglandular dysfunction	ICD-10: E31*	
Polyarthritis nodosa	ICD-10: M30.0-M30.2	
Rheumatoid arthritis	ICD-10: M05*-M14*	
SLE and other systemic connectivity tissue disorders	ICD-10: M32.1, M32.8, M32.9, M33*, M34* (excluding M34.2), M35.0	Includes dermatopolymyositis, systemic sclerosis and Sjögren's syndrome
Inflammatory bowel disease	ICD-10: K50*, K51*	Crohn disease, ulcerative colitis
Epilepsy	ICD-10: G40*, G41*	Epilepsy, status epilepticus
Multiple sclerosis	ICD-10: G35*	
Hypertension	ICD-10: I10*-I15*	Hypertensive diseases
Ischemic heart diseases	ICD-10: I20*-I25*	
Chronic heart diseases	ICD-10: I27*, I31*, I34*-I37*, I39*, I42*, I52*	Other pulmonary heart diseases, other diseases of pericardium, heart valve disorders, cardiomyopathy, other heart disorders in diseases classified elsewhere
Cerebrovascular diseases	ICD-10: I60*-I69*	
Atherosclerosis	ICD-10: I70*	
Coagulation disorders	ICD-10: D66*-D68*	Hereditary factor VIII deficiency, hereditary factor IX deficiency, other coagulation defects
Chronic lung disease	ICD-10: J40*-J47*, J60*-J70*, J84*	Chronic lower respiratory diseases, lung diseases due to external agents, other interstitial pulmonary diseases
HIV	ICD-10: B20*-B24*	
Mood disorders	ICD-10: F30*-F39*	
Schizophrenia, schizotypal and delusional disorders	ICD-10: F20*-F29*	
Neurotic, stress-related and somatoform disorders, specific personality disorders	ICD-10: F40*-F48*, F60*	

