Pervasive developmental disorders	F84* (excluding F84.2, F84.3, F84.4)	
Antidepressants	ATC: N06A	

Variable	Code ⁺	Comment
Antipsychotics	ATC: N05A	
Anxiolytics	ATC: N05B	
Hypnotics and sedatives	ATC: N05C	
Medical history, laboratory test results[#]		
Anti-Müllerian hormone	NPU27675 NPU27385	
FSH	NPU04014 NPU02072 NPU02073	
Thyrotropin	DNK05280 NPU04026 NPU04199 NPU10347 NPU10374 NPU04200 NPU08717 NPU04202 NPU19580 NPU29633 NPU03577 NPU27547 NPU28066 NPU28065 NPU03751	
Prolactin	NPU21694 NPU04022 NPU04021 NPU18247 NPU03252 NPU26171 NPU26172 NPU26173 NPU26174 NPU22291 NPU22292 NPU26175 NPU22293 NPU26176 NPU26177 NPU26178 NPU19897 NPU10458 NPU10460 NPU10682	

ATC: Anatomical Therapeutic Chemical; COS: controlled ovarian stimulation; FSH: follicle-stimulating hormone; ICD-10: International Classification of Diseases, 10th revision; HIV: human immunodeficiency virus; IVF: in vitro fertilization; NOMESCO: Nordic Medico-Statistical Committee; NPU: Nomenclature for Property and Unit; PCOS: polycystic ovarian syndrome; rhFSH: recombinant human follicle-stimulating hormone; SAP: statistical analysis plan; SLE: systemic lupus erythematosus.

Notes:

⁺Country-specific adaptations may be made at the data permit stage. Conditions defined by ICD-10 codes are considered present if there was a record of a primary or secondary diagnosis in the national (patient) registers (outpatient or inpatient care). Similarly, procedures defined by NOMESCO codes are considered to have been

performed if there was a record in the national patient registers (outpatient or inpatient care). Based on dispensing records in the prescribed drug registers for drugs defined by the listed ATC codes, it is assumed a given drug was used.

*All ATC, ICD-10, or procedure subcodes are included.

#Available for Denmark only.

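### Smoking and the register's female, male and idiopathic infertility classes enter the propensity score only in Denmark, the shared female infertility code contradicts its own definition, and nothing checks what unequal adjustment does to the combined odds ratio

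*Protocol*

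**What the plan says.** Table 1 in section 9.3.2 lists "Smoking status" and "Male factor infertility", together with female and idiopathic factor infertility, as PS candidates. Each carries an asterisk, which the table note explains as "Available for Denmark only (from the DIVF").

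Section 9.9.3 concedes that "differences in baseline characteristics, e.g., in terms of cause of infertility or previous IVF treatment, between the study cohorts cannot be ruled out" and relies on weighting over a broad set of characteristics to limit the resulting confounding. Section 9.7.3.1 says the weights deal with covariates included in the PS model. Section 9.9.4 gives antral follicle count and anti-Müllerian hormone as predictors missing in Sweden. Section 9.1.1, after describing how alike the registers are, says "The same type of analyses can therefore be performed in both countries, with little need for adaptation".

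In the code list of section 14.3.3, the female infertility row reads "ICD-10: E28.3, E28.8, E28.9, N97", with an asterisk on N97. The note to the list says of the asterisk: "All ATC, ICD-10, or procedure subcodes are included". The comment in the same row describes the variable as including "female infertility (excluding female infertility associated with male factors").

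On pooling, section 9.7.3.8 says that the country results will be combined and, in the next sentence, that an aggregate-data meta-analysis will be considered. The abstract and sections 9.1.1 and 9.7 say that it may be.

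**The concern.** Weighting balances only what is in the score. The protocol's own first example of a likely cohort difference is cause of infertility, yet a central part of that information is absent from one of the two countries. A Danish and a Swedish odds ratio would then estimate the same contrast after different confounder control. If they differ, a reader cannot separate a difference in effect from a difference in adjustment. If they agree and are pooled, the summary carries whatever Swedish confounding is left.

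The N97 conflict adds to this. Taken literally, the code records women whose infertility is attributed to male factors as having female infertility. Denmark has a separate male-factor variable to offset that error; Sweden has none listed.

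**Working it through.** **1. Which covariates each country has (Table 1).**

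| PS candidate | Denmark | Sweden |
|---|---|---|
| Smoking status | yes | no |
| Female factor infertility (register) | yes | no |
| Male factor infertility (register) | yes | no |
| Idiopathic factor infertility (register) | yes | no |
| Female infertility diagnosis (ICD-10) | yes | yes |
| PCOS, endometriosis, amenorrhea/oligomenorrhea | yes | yes |
| Treatment type (IVF, ICSI) | yes | yes |

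Sweden keeps several female causes, and treatment type may stand in partly for male factor. It has no direct male-factor, idiopathic-factor or smoking variable.

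**2. Code against definition (section 14.3.3).** The row includes every N97 subcode, while its comment removes a male-factor-associated part. Both cannot be applied. Where the authors wanted an exclusion elsewhere in the table, they wrote it into the code: the adrenal row excludes E27.2, E27.3 and E27.5, and the pervasive developmental disorder row excludes F84.2, F84.3 and F84.4. The female infertility row names no excluded subcode.

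**3. The protocol's own scale.** Section 9.5 gives 1.5 points as detectable against HP-hMG, at a 50% comparator rate with 75% of women eligible. The log odds ratio is ln[(0.515/0.485)/(0.5/0.5)] = 0.0600, so OR = 1.062. The standard error is √[1/(n₁p₁(1−p₁)) + 1/(n₀p₀(1−p₀))].

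- Denmark, 0.75 × 19,000 = 14,250 vs 0.75 × 12,000 = 9,000: SE 0.0269, lower limit exp(0.0600 − 1.96 × 0.0269) = 1.007.
- Sweden, 0.75 × 18,000 = 13,500 vs 0.75 × 17,000 = 12,750: SE 0.0247, lower limit 1.012.

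A 1.0-point difference fails in both countries, so 1.5 is reproduced on the 0.5-point grid.

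**4. Would the heterogeneity check reveal unequal adjustment?** Section 9.7.3.8 flags I² ≥ 50% or P < 0.1. With two countries I² = (Q − 1)/Q, so I² ≥ 50% means Q ≥ 2, and P < 0.1 means Q > 1.645² = 2.71. The rule therefore reduces to Q ≥ 2, that is |z| ≥ 1.414. Suppose, for scale only, that one country carries 1.5 points of extra bias and the true effects are equal. Standard errors below are taken at 50% in both cohorts.

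- HP-hMG comparison: SE of the difference √(0.0269² + 0.0247²) = 0.0365; z = 0.0600/0.0365 = 1.64; chance of a flag about 59%.
- Biosimilar comparison (10,500 vs 2,250 in Denmark; 8,250 vs 7,500 in Sweden): SE 0.0564; z = 1.06; chance about 37%.
- No bias: about 16%.

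These use unweighted standard errors; variance inflation from weighting would lower the first two. A flag leads only to review and discussion.

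**5. What imbalance would matter?** For one binary confounder, bias in points ≈ (effect on live birth) × (prevalence difference between cohorts left after the other covariates). Neither term is in the protocol. Assuming effects of 5, 10 or 15 points, a spurious 1.5-point difference needs a residual imbalance of 1.5/5 = 30, 1.5/10 = 15 or 1.5/15 = 10 points.

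**The case against.** The strongest reply is that this is a limit of the data, not an error of planning, and that it is disclosed. Table 1 shows the asterisks; section 9.9.4 introduces its two predictors as examples and then says that unmeasured confounding cannot be ruled out; section 9.9.3 claims to minimize confounding, not to remove it. Pooling is partly worded as optional, heterogeneity is assessed first, country results are always reported, and meta-analysis details are left to the SAP. Section 14.3 allows the code lists to be revised. Much of this stands, and it keeps the point modest. It does not settle which reading of N97 applies, and it does not supply a check that the Danish data could provide.

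Three stronger readings are tempting and not supported:

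- That Sweden has only one infertility-cause variable, or cannot adjust for cause at all. Section 1 of the working shows otherwise.
- That the N97 conflict is a Swedish fault. The code list serves both countries.
- That the bias can be put as a share of the detectable difference. Any such figure needs assumed prevalences, effects and directions, and biases from smoking and male factor could partly cancel.

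Section 9.7.2 mentions smoking being recorded in the IVF registries without limiting this to Denmark. If Sweden does hold it, the gap is smaller and the Table 1 note needs correcting.

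**Conclusion.** The point holds as a moderate one. Three things follow from the text alone: the two scores cannot contain the same confounders; the female infertility code and its comment are incompatible; and section 9.7.3.8 foresees combining the country estimates with no check on unequal adjustment, while section 9.9.4 leaves the Swedish gap unnamed.

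That the Swedish odds ratios are more confounded is a reasonable inference, not a demonstrated fact. It depends on the four missing variables differing between drug cohorts and predicting live birth after the available substitutes are taken into account. No magnitude can be claimed from the document. The arithmetic shows only that the heterogeneity check cannot be relied on: it would miss a 1.5-point discrepancy in about 41% of cases (100% − 59%) for HP-hMG and 63% (100% − 37%) for biosimilars, under the assumptions stated.

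**What to change.** 1. **Section 14.3.3:** replace the all-subcodes N97 entry with an explicit list that leaves out the male-factor-associated subcode, as the comment intends. Consider that subcode as a separate marker in the Swedish PS if its completeness allows. Settle this early, because the notes place country adaptations at the data permit stage.
2. **Table 8:** add a Danish re-estimation of the primary odds ratios using only the covariates available in Sweden, with the same outcome model, reported beside the full-set odds ratios. This shows what the missing variables do in Denmark; carrying it over to Sweden assumes similar prescribing patterns.
3. **Section 9.7.3.8:** if a meta-analysis is done, show the pooled odds ratio on the common covariate set as a sensitivity result. Keep the full-set version as main, so that valid Danish confounder control is not given up.
4. **Section 9.9.4:** name smoking and the register classification of infertility cause as unavailable in Sweden, and reconcile the Table 1 note with section 9.7.2 on smoking.

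The cost is a code-list edit, a few sentences and one extra weighted run per primary outcome in Denmark. No new data are needed for the Danish re-run.

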9.4 Data Source

The Danish and Swedish data sources are the property of, maintained and made accessible for research by permission of governmental and regional authorities. The health care system is a tax-funded, one-payer system with coverage for all residents and only little co-payment from the patients.

Since introducing the Danish Civil Registration System in 1968, demographics (age, sex, geographical region), migration and vital statistics data have been registered electronically on a daily basis for all Danish residents. Civil registration in Sweden dates back to the 17th century and was transferred from the local parishes to the state in 1991. Demographic data (age, sex, geographical region), migration and vital statistics data for all Swedish residents can be found in the Total Population Register (held by Statistics Sweden) from 1968 onwards.

Every individual in Denmark and Sweden is provided with a unique personal identification number at birth or upon immigration which allows for follow-up until death or emigration. The personal identification number is used for many administrative purposes, such as an identifier in population and health care registers.

The personal identification number forms the basis for the precise, deterministic linkage of individual-level data between different registers and databases in Denmark and Sweden. Given that the personal identification number is used as a unique identifier for a multitude of purposes, it allows for the creation of a tailored database with individual-level data for any given study.

The Danish and Swedish health care data sources are typically established as registers for other reasons than research (examples: control and funding of hospitals, payment of general practitioners for services provided to patients, control system for patients' co-payment of prescription drugs, and authorities' control of treatments using assisted reproduction techniques). Thus, the registers are a mirror of clinical practice in each country. Furthermore, the data sources are also used extensively for epidemiological research.

The DIVE, the Civil Registration System (CPR), the Danish Medical Birth Register (DMBR), the Danish National Patient Register (DNPR), the Danish Register of Medicinal Product Statistic (RMPS), the Q-IVF, the Swedish Medical Birth Register (SMBR), the Swedish National Patient Register (SNPR), the Swedish Prescribed Drugs Register (SPDR) and Swedish Cause of Death Register are the databases for identification of the study population and extraction of exposure, covariate and outcome variables. Thus, the information needed is assembled by linkage of several health care registers using the unique personal identification number.

9.4.1 Denmark

The Civil Registration System (CPR) holds base information on personal identification number, date of birth, sex, immigration/emigration dates, ethnicity/country of origin, date of death, etc. since 1970.

The Danish In-vitro Fertilization Register (DIVE) was established to provide evidence for the Danish National Board of Health's monitoring of ART treatments in Denmark as well as providing data for research. The register contains information on ART treatments at both public and private fertility clinics in Denmark, including the cause of the infertility, fertilization method, origin of semen and oocytes, and vitrification methods. Pregnancy outcome is not recorded. The DIVE has been in operation since 1994, with later improvements in 2006. Starting from this year, information was added on, e.g., IUI, the woman's and partner's life style (weight, alcohol and smoking habits), results from ultrasound examination, including number of gestational sacs with/without heartbeat, choice of cryopreservation method, and whether transfer of one embryo only (fresh or frozen) was an elective or non-elective procedure. The register is updated monthly.

It is possible to submit changes to already reported information. With a lag of approximately 2 months, it is estimated to capture the majority of subsequent changes to already reported information.

The Danish National Patient Register (DNPR) contains information on the Danish population's encounters at hospitals (secondary care) (28,29). The register is a central tool for the health care authorities to monitor diseases and treatments, and the activities at the individual hospitals. Data on activities and diagnoses in primary care at general practitioners (GPs) and specialists in private practice is not included. The register contains information on date of admission and discharge, type and setting of care (inpatient or outpatient), diagnoses (classified according to the ICD-10 classification), examinations, surgical and non-surgical procedures, and Diagnosis Related Group (DRG) costs. Data is available from 1977 for inpatient somatic admissions. Since 1995, outpatient visits, emergency room visits and encounters at psychiatric wards are also included. DRG costs are available since 2002.

The Danish Medical Birth Register (DMBR) is an enrichment of data already recorded in the DNPR and compiles relevant information of pregnancies that has led to childbirth in Denmark at home or in a hospital (30). It contains information on characteristics of mother and child, pregnancy and delivery characteristics including induction procedures and gestational age, outcomes of pregnancy and delivery, and the mother's history of previous abortions and/or deliveries. The DMBR includes linkage between infant, mother and father. The DMBR has been in operation since 1973, with later improvements, particularly in 1997. The register is updated once a year after end of December with a lag of 13 months, partly due to the enrichment on information on date of death within the first year after birth.

The Danish Register of Medicinal Product Statistics (RMPS) contains patient-level data on all prescription drugs filled by patients at community pharmacies (31,32), but not medication administered at hospitals. The administrative purpose of the register is to administer how the cost is split between the health care system, the municipality and the patient's co-payment. Thus, completeness and accuracy of data collection is very high. The register contains information on the date of purchase, item number, product name, ATC code, strength per unit, quantity of DDDs (as per the World Health Organization (WHO)) per package and number of packages filled. Data is available from 1995 and onwards. Since April 2004, information on medical indication for prescription and daily prescribed dose by physician has also been available, but completeness and validity are affected by a non-compulsory obligation to record this information.

The Danish Register of Laboratory Results for Research (RLRR) is managed by the Danish Health Data Authority. It has information on laboratory tests at the country's major clinical biochemical and clinical immunological laboratories. Laboratory results are first collected in the National Lab Databank. General practitioners, specialists in private practices and private fertility clinics can forward samples for analysis to the hospital laboratories, when they do not have the capacity/equipment to do the analysis themselves, and these tests are also included in the National Lab Databank. All this information is transferred to the RLRR later. If a patient, proactively, has denied consent to exchange lab results, the results are not transferred to the RLRR.

Since 2013, the five regions in Denmark has gradually started transferring data to the Danish National Lab Databank,, and subsequently the RLRR, but some historical data has also been

transferred to the National Lab Databank. The National Lab Databank does not cover the whole nation yet, since all laboratories are not affiliated, and completeness is not reported. However, of all laboratory test results coded with NPU codes across the affiliated laboratories, 95% are currently in the National Lab Databank.

Two types of tests are included in the National Lab Databank : a) analysis of blood, urine, joint fluids and spinal fluids for the purpose of preventing, diagnosing and controlling the treatment of human diseases; b) blood type determination and examination of blood in, e.g., pregnancy, immune disorders and certain infections. The National Lab Databank contains information on type of test, value, unit, and date of sample collection.

Only laboratory tests encoded with Nomenclature for Property and Unit (NPU) terminology (that is, codes beginning with either “NPU” or “DNK”) is transferred from the National Laboratory Databank to the RLRR. RLRR is updated weekly from the National Laboratory Database.

